## 2 Study Objectives

## 2.1 Primary Objective(s)

The primary objective of this study is to observe the rate of recovery of ventricular function (EF>35%) between 90 and 180 days in newly diagnosed HF with reduced EF patients who were prescribed the WCD while being initiated on their HF medications. This will be measured from EF closest to before hospital discharge, then at 90, 180 and 360-days after WCD start, regardless of continued WCD use, prior EF improvement, or ICD implantation. While approximately one-third of the patients will likely experience EF recovery in the first 90 days, we hypothesize that an additional 5-10% of patients will experience EF improvement between 90 and 180 days as GDMT is achieved. This would be considered clinically significant in terms of the potentially avoided ICD implantations. Outcomes will be tracked and reported for three pre-specified groups based on assessment of SCD risk at 90 days of WCD use:

- 1) Patient improved (EF >35%), SCD risk deemed to be negligible. These patients are expected to end WCD use and not receive an ICD.
- 2) Patient improved EF from start of WCD use (a positive change of at least 5 percentage points in EF), or has a borderline EF of 30-35%, but still has continued SCD risk (EF ≤ 35%). These patients are expected to continue to use the WCD for an additional 3 months.
- 3) Patient not improved from start of WCD use (no change or worsening of EF), EF<30% and has continued high SCD risk. Those on GDMT are expected to be evaluated for an ICD. Those not yet on GDMT may continue the WCD for an additional 90 days.

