#### 3.2.2 LVEF recovery

To support our primary hypothesis that an additional 5% of patients will experience EF improvement between 90-180 days, EF measurement for all patients at 90 (±14), 180 (±14) and 360 (±14)-days after WCD start will be requested and recorded. For this study, EF>35% will be considered as EF improved.

- 3.2.2.1 Echocardiographic assessment of LVEF is most common. Nevertheless, other imaging modalities (MUGA, MRI) may be used to document LVEF at day 0. Although there are likely to be differences in EF assessment among enrolling sites and practices, these differences are not expected to affect the outcome of the trial. At a minimum, we will request a 2-D, M-mode echo at the scheduled time-points.
- 3.2.2.2 Echocardiogram core lab verification. EF is commonly estimated by echocardiogram. Several studies have shown EF measurement to have a wide range of variability that can be observer dependent. Study echocardiograms will be sent to a core lab for a uniform determination of the EF. The core lab determinations will be used to verify local estimates of EF and may be used in secondary analyses of the study data

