6.2.2 Visit post-index hospitalization (day 0 - 30 from WCD start)

- 6.2.2.1 Inclusion/exclusion will be verified.
- 6.2.2.2 Informed Consent for registry will be obtained.
- 6.2.2.3 Clinical history data will be collected, including current Echo and ECG data.
- 6.2.2.4 Medication usage will be collected
- 6.2.2.5 QOL data will be collected (subset of patients only)

The following scheduled visits are for all study patients, regardless of ongoing WCD use, and include:

- 6.2.3 Visit 1 Enrollment (day 90 ± 14 from WCD start)
  - 6.2.3.1 Inclusion/exclusion will be verified.
  - 6.2.3.2 Informed Consent will be obtained.
  - 6.2.3.3 Clinical data will be collected, including current Echo and ECG data.
  - 6.2.3.4 Medication usage will be collected and any adjustments made to achieve GDMT.
  - 6.2.3.5 QOL data will be collected (subset of sites only)

For patients who will be continuing WCD use only:

6.2.3.5 Medical orders and dispensing of the WCD will follow current commercial procedures.

 Spertus and Jones. Development and Validation of a Short Version of the Kansas City Cardiomyopathy Questionnaire. Circ Cardiovasc Qual Outcomes. 2015;8:00-00.

6.2.4	Patient intervi	lews through follow-up phone calls or office visits (days 120 $\pm$ 14 and 150 $\pm$ start)
	6.2.4.1	Clinical data will be collected
	6.2.4.2	Medication changes will be collected
	6.2.4.3	Device information, adverse events, and cardiac event information will be collected as needed
6.2.5	Visit 2 (day 18	30 ± 14 from WCD start)
	6.2.5.1 6.2.5.2	Clinical data will be collected, including current Echo.  Medication changes will be collected.
	6.2.5.3	Device information, adverse events, and cardiac event information will be collected.
	6.2.5.4	If patient has recently ended the study, or WCD use, reasons will be collected.
	6.2.5.5	QOL data will be collected (subset of patients only)
6.2.6	Patient intervi	iew through follow-up phone calls or office visits (day 270 $\pm$ 14 from WCD
	6.2.6.1	Clinical data will be collected.
	6.2.6.2	Medication changes will be collected.
	6.2.6.3	Device information, adverse events, and cardiac event information will be collected.
	6.2.6.4	If patient has recently ended the study, or WCD use, reasons will be collected.
6.2.7	Visit 3 (day 36	60 ± 14 from WCD start)
	6.2.7.1	Clinical data will be collected, including current Echo.
	6.2.7.2	Medication changes will be collected.

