## 8.3 Endpoint Assessment

## 8.3.1 Primary Endpoint – LVEF recovery and GDMT

Descriptive or summary statistics of serial EF measurements will be used to analyze the rate of recovery of ventricular dysfunction following discharge. For example, the means of EF at 180 days will be compared to the means of EF at baseline and 90 days. The percentage of patients reaching the goal of EF>35% will be compared at 90 days and 180 days. Also, the time taken to reach EF>35% will be calculated for those who improve, and compared between groups (based on baseline characteristics). Individual patient EF measurements over time will be compared to determine whether common patterns arise in certain groups of patients (fast recovery/slow recovery, plateaued recovery/peaked recovery followed by decline). The influence of baseline characteristics on the potential for recovery will be evaluated.

Descriptive statistics will be used to assess the degree GDMT was reached at 90 and 180 days, and how GDMT relates to EF recovery. We will also assess how adherence to the GDMT regimen affects EF recovery and overall clinical improvement.

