#### 8.4 Statistical Methods

All analyses have been described elsewhere in the protocol.

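### The GDMT and adherence comparisons of recovery past a fixed EF of 35% take no account of starting EF, so a group that starts nearer the line can appear to recover more often with the same EF gain

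*Combined protocol and SAP*

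**What the plan says.** Section 3.2.2 sets a fixed threshold: "For this study, EF>35% will be considered as EF improved". Entry (4.1.2, 4.1.4) requires only that EF was 35% or lower during the index hospitalization, so patients start at varying distances below the line.

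Starting EF is collected. Section 2.1 says of recovery: "This will be measured from EF closest to before hospital discharge, then at 90, 180 and 360-days after WCD start". Section 6.2.2 adds, at registry entry, "Clinical history data will be collected, including current Echo and ECG data".

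Three sentences in 8.3.1 relate recovery to patient factors:

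- On GDMT: "Descriptive statistics will be used to assess the degree GDMT was reached at 90 and 180 days, and how GDMT relates to EF recovery".
- On adherence: "We will also assess how adherence to the GDMT regimen affects EF recovery and overall clinical improvement". No method is given.
- On baseline factors: "The influence of baseline characteristics on the potential for recovery will be evaluated". No method is given.

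None names a model, covariate or stratifier. Section 8.4 reads in full "All analyses have been described elsewhere in the protocol", and 8.5 is marked not applicable. Sections 3.1.1 and 8.2 state that there is no randomization.

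**The concern.** Whether a patient passes 35% depends on the gain in EF and on how far below 35% the patient began. GDMT achievement and adherence are not randomized, so nothing in the design makes their groups alike in starting EF. If one group starts higher, a crude comparison of the percentage above 35% credits GDMT or adherence with recovery that reflects the starting point. If the better-treated group starts lower, the same mechanism can hide a real association.

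This matters because 3.2 names GDMT and EF recovery as the two primary endpoints, and 3.1 frames the hypothesis as recovery that occurs while GDMT is being achieved. The link between them is what readers will take from 8.3.1, and the adherence sentence words it as an effect.

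**Working it through.** **The plan's own figure.** There is none on this point. The only calculation, in 8.1.1, is a one-sample test of a single proportion. It contains no between-group term, so starting EF does not enter it.

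**Inputs.** From the documents: recovery line 35 (3.2.2) and starting EF of at most 35 (4.1). The documents give no mean or SD for EF, so the rest is assumed: starting EF normal with SD 5 or 6, truncated to 10–35; EF gain normal and identical in both groups, with mean (SD) of 4 (6), 5 (8) or 6 (8).

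**Formula.** For a patient starting at EF b, with gain mean g and SD s:

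P(EF>35) = 1 − Φ((35 − b − g)/s)

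**One patient at a time** (a further assumed gain, mean 8, SD 8):

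- b = 20: (35 − 20 − 8)/8 = 0.875, so P = 19%
- b = 25: (35 − 25 − 8)/8 = 0.25, so P = 40%
- b = 30: (35 − 30 − 8)/8 = −0.375, so P = 65%

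The gain distribution is the same in all three lines.

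**Two groups.** Average the formula over each group's starting EF. The higher group has nominal mean 28 (about 27 after truncation). The lower has nominal mean 26, 24 or 22. Ranges run over the two starting SDs and the three gains.

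| Gap in mean starting EF | Recovered, lower group | Recovered, higher group | Apparent ratio |
|---|---|---|---|
| about 1.5 points | 24–36% | 29–42% | 1.16–1.28 |
| about 3 points | 18–29% | 29–42% | 1.4–1.7 |
| about 5 points | 12–24% | 29–42% | 1.7–2.5 |
| none | equal | equal | 1.0 |

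**Does adjustment remove it?** Simulation, 1,000 runs per setting, gain mean 8 and SD 8 in both groups, starting SD 6 before truncation, mean starts 26.0 and 23.7. An unadjusted two-proportion test at the 5% level declared a difference in 30% of runs with 120 per group and 56% with 250 per group. Logistic regression on starting EF, or ANCOVA of follow-up EF on starting EF, gave about 5%. With equal starts all three gave about 5%.

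**Which starting EF?** Pre-discharge EF precedes the follow-up therapy being compared. Day-90 EF does not: it may already reflect GDMT and adherence in the first 90 days. Two illustrative simulations, each with adherence adding 4 points by day 90 and nothing later plus an unmeasured tendency to recover, show the consequence. Both fitted the factor and day-90 EF among patients at or below 35% at day 90.

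- In one, the odds ratio for adherence was about 0.8 although adherence raised day-180 recovery from 41% to 54%.
- In the other, starting EF was normal (25, SD 6, truncated to 10–35). The gain to day 90 was 4, plus 4 if adherent, plus u, plus noise of SD 5. The further gain to day 180 was 2, plus u, plus noise of SD 5, with u of SD 4. The odds ratio was 0.77 although recovery rose from 35% to 48%.

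**Precision.** For continuous EF, a comparison with 50% unadjusted power (z = 1.96) and correlation 0.5 between starting and follow-up EF would reach Φ(1.96/√0.75 − 1.96) = 62% if the factor were unrelated to starting EF. The bias exists only when it is related. With a 5-point gap, equal groups and SD 5, the squared correlation of factor with starting EF is 2.5²/(2.5² + 5²) = 0.20. Power becomes Φ(1.96 × √(0.80/0.75) − 1.96) = 53%. At correlation 0.3 it is Φ(1.96 × √(0.80/0.91) − 1.96) = 45%, below the unadjusted 50%.

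**The case against.** The other side has real points.

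- **Partial coverage.** Table 1 in 6.5 lists echo among the baseline data, so starting EF can be read as one of the baseline characteristics to be evaluated. Section 2.1 reports outcomes in three day-90 groups built largely from EF, a coarse stratification. Section 8.3.1 also compares mean EF over time and looks at individual EF courses, neither of which depends on the cut-off. This stands, and it narrows the gap. It does not close it: examining EF as a separate predictor, or averaging EF over time, does not adjust the GDMT or adherence comparison.
- **No primary test is touched.** A reader might infer that the main hypothesis is biased. It is not. The test in 8.1.1 is single-group, and the endpoints in 3.2 are not themselves between-group contrasts.
- **Crude subgroup rates are legitimate.** A reader might infer that every unadjusted comparison in 8.3.1 is misleading. A baseline subgroup that starts higher does cross 35% more often, and that is a proper description given the interest in 2.1 in avoided implants. The problem lies in attributing recovery to GDMT or adherence.
- **The size is assumed.** This stands. A 5-point gap is about one SD of starting EF. If follow-up EF rises only half a point per point of starting EF, the ratio for that gap falls to about 1.4–1.8.

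**Conclusion.** The concern holds for two comparisons in 8.3.1: recovery by GDMT and recovery by adherence. Both concern a fixed threshold in a non-randomized study, and no account of starting EF is planned for either. On the assumed EF values the apparent ratio with no difference in gain is about 1.2, 1.4–1.7 or 1.7–2.5 for gaps of about 1.5, 3 or 5 points. These ratios also assume that gain does not depend on starting EF. The documents do not show that any imbalance exists or which way it would run; with balanced starting EF this bias is absent.

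Two further readings are tempting and not supported. Adjustment should not be presented as a gain in power: where the bias is present, most or all of that gain is lost, and the plan powers no such comparison. Nor is day-90 EF a safe covariate for the main comparison, because it may itself result from the therapy being assessed.

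**What to change.** In 8.3.1:

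1. Report the GDMT and adherence comparisons of EF>35% at days 90 and 180 from a logistic model with pre-discharge EF (continuous) and ischemic or nonischemic etiology as covariates. Show crude percentages alongside.
2. Compare mean EF between the same groups by ANCOVA on pre-discharge EF, again with crude means alongside.
3. Replace *affects* in the adherence sentence with *is associated with*.
4. Make any days 90–180 analysis that is restricted to EF of 35% or lower at day 90 and adjusted for day-90 EF secondary. Use only GDMT or adherence after day 90 as its factor, and state that day-90 EF may itself result from earlier therapy.

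The single-group test and the descriptive rates by baseline subgroup stay as they are.

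The cost is SAP wording and some extra analysis of data already planned; no visit or patient is added. Residual confounding will remain from unmeasured factors and from EF measurement error, which 3.2.2.2 acknowledges can be wide, and the report should say so.

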#### 8.3.2 Secondary Endpoint- Treatments by the WCD or ICD

Treatment events will be initially determined to be appropriate or inappropriate by each site's principal investigator. All shocked events and terminal ECG recordings will be adjudicated by a committee independent of the sponsor.

Effectiveness of the WCD in treating ventricular arrhythmias will be evaluated through descriptive means. Clinical outcomes and device data from any defibrillation or cardiac event will be reviewed for success as defined by appropriate detection and defibrillation, conversion out of the detected ventricular arrhythmia, and consciousness when medically evaluated after treatment.

Descriptive statistics will be used to analyze the incidence of unnecessary shocks from WCD and ICD in this population. Causes of prolonged false detections and lack of response button use in WCD users will be reviewed.

8.3.3 Secondary Endpoint- Incidence of all untreated sustained VT/VF events during WCD use not associated with a shock event (i.e. not within 24 hours of shocked VT/VF event).

Descriptive statistics will be used to analyze the incidence of untreated sustained (≥ 30 seconds) episodes of VT or VF. All possible reasons for a lack of shock will be reviewed, including response button use, rate threshold settings, or ECG artifact. ECG recordings will be adjudicated by a committee independent of the sponsor.

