## 2.2 Secondary Objective(s)

The specific secondary objectives are to:

2.2.1 Observe the incidence and etiology of SCA and all sustained VT/VF arrhythmias during WCD use.

- 2.2.2 Observe the incidence of other arrhythmias during WCD use, such as asystole and supra-ventricular arrhythmias that are recorded by the device.
- 2.2.3 Collect ICD treatment data for those who receive an ICD, and evaluate for appropriateness.
- 2.2.4 Observe the effectiveness of the wearable defibrillator worn by this population in treating ventricular arrhythmias. Clinical outcomes data from any defibrillation or cardiac event will be collected, including device data on appropriate arrhythmia detection and shock delivery.
- 2.2.5 Evaluate the effect of wearable defibrillators on 90,180, 270, and 360-day mortality following WCD start in HF patients. Assessment of survival will be made at these time points for those entered into the study. A mortality review will be conducted to group all deaths as cardiac or non-cardiac, and sudden or non-sudden.
- 2.2.6 Collect economic and healthcare utilization data on all patients.

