## 3.3 Secondary Study Endpoints

The secondary endpoints are observational and include documentation of any SCA/SCDs, including any treatments by the WCD or ICD, any untreated sustained ventricular arrhythmias that are recorded by the WCD, and the mortality following discharge in HF patients. We will also collect economic and healthcare utilization data on all patients.

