3.3.1 SCA/SCD, Sustained Ventricular Arrhythmias, and Mortality

3.3.1.1 "Sudden Cardiac Death" will be defined as an unexpected, non-traumatic, non-self-inflicted fatality in otherwise stable subjects who die within one hour of the onset of the terminal symptoms. Subjects dying more than one hour after a sudden cardiac arrest (SCA) from a ventricular arrhythmia will be designed as non-sudden death due to ventricular arrhythmia. For unwitnessed deaths participants will meet the definition of sudden cardiac death if they are found dead within 24 hours of being well, assuming there is no evidence of another cause of death during that time period. Autopsy results may be used when available.

For the mortality analysis, all deaths will be classified by the site investigator as cardiac or non-cardiac, and sudden or non-sudden.

- 3.3.1.2 "Appropriate detection" will be defined as a device alarm/detection during a ventricular tachyarrhythmia.
- 3.3.1.3 "Sustained ventricular arrhythmia" will be defined as any WCD-recorded appropriate detection with ≥ 30 seconds of uninterrupted VT/VF.
- 3.3.1.4 "Appropriate treatment" will be defined as a therapy shock or anti-tachycardia pacing (ATP) given during a ventricular tachyarrhythmia.
- 3.3.1.5 "Inappropriate treatment" will be defined as a therapy shock and/or ATP (for ICD recipients) delivered in the absence of an appropriate detection.
- 3.3.1.6 "Other treatment" will be defined as a therapy shock delivered during an appropriate detection but on a section of the recording not showing a ventricular arrhythmia.
- 3.3.2 Effectiveness of the wearable defibrillator in treating ventricular arrhythmias

Clinical outcomes and device data from any defibrillation or cardiac event will be reviewed for success as defined by appropriate detection and defibrillation, conversion out of the detected ventricular arrhythmia, and consciousness when medically evaluated after treatment.

- 3.3.3 Incidence of other WCD recorded arrhythmias, such as asystole and supra-ventricular arrhythmias.
- 3.3.4 Economic and healthcare utilization data on all patients

Information (days, reasons) on any hospitalizations, emergency room visits, observation stays, urgent care visits, other physician office visits, and stays at skilled nursing facilities.

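### Section 8.3.3 drops untreated sustained VT/VF within 24 hours of a shocked event, although 2.2.1 and 3.3 set no such limit, and the plan conflicts on whether recorded but unflagged VT/VF counts

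*Combined protocol and SAP*

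**What the plan says.** Section 2.2.1 states the objective without qualification: "Observe the incidence and etiology of SCA and all sustained VT/VF arrhythmias during WCD use". The endpoint overview in 3.3 adds "any untreated sustained ventricular arrhythmias that are recorded by the WCD"; its only limit is that the WCD must have recorded the episode.

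Section 3.3.1.3 defines a sustained ventricular arrhythmia as "any WCD-recorded appropriate detection with ≥ 30 seconds of uninterrupted VT/VF". Section 3.3.1.2 defines an appropriate detection as "a device alarm/detection during a ventricular tachyarrhythmia".

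The heading of 8.3.3 limits the untreated endpoint to events "not associated with a shock event (i.e. not within 24 hours of shocked VT/VF event". The text beneath it describes sustained episodes by duration (30 seconds or more), does not mention detection, and continues: "All possible reasons for a lack of shock will be reviewed, including response button use, rate threshold settings, or ECG artifact". These recordings go to an independent adjudication committee.

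Section 6.3.1.1 has the sponsor notify sites, and send ECG strips, when a recording shows a shock, VT/VF of more than 30 seconds without a shock, or asystole. It makes no exception for episodes close to a shock.

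**The concern.** There are two problems.

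First, the analysis is narrower than the objective it serves. Read literally, the 24-hour rule works in both directions: it removes an unshocked episode that precedes a shock and an unshocked recurrence that follows one. The plan gives no reason for the rule. If it is a clustering convention, the plan does not say so and does not define the event unit in 8.3.2 that would absorb the clustered episodes.

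Second, the plan is unclear on whether VT/VF that appears on a recording, but that the device did not flag, is a sustained arrhythmia at all. Under 3.3.1.3 it is not. Under 8.3.3 it seems to be, since rate thresholds and artifact can be causes of non-detection and are listed among the reasons to review.

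At stake is the reported incidence under 2.2.1. The second point also bears on 2.2.4, which asks about arrhythmia detection: a case definition that presupposes detection cannot show a failure to detect.

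**Working it through.** The plan gives no figure for this endpoint, so the check is a comparison of sections.

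| Section | What it covers | 24-hour limit | Device detection required |
|---|---|---|---|
| 2.2.1 objective | Sustained VT/VF while the WCD is in use | None | Not stated |
| 3.3 endpoint overview | Untreated sustained arrhythmias on WCD recordings | None | Not stated here |
| 3.3.1.3 definition | Uninterrupted VT/VF of at least 30 seconds | None | Yes, through 3.3.1.2 |
| 6.3.1.1 notification | Unshocked VT/VF of more than 30 seconds on a recording | None | Not stated |
| 8.3.3 analysis | Unshocked VT/VF of at least 30 seconds | Excluded within 24 hours of a shocked event | Not stated; threshold and artifact are reviewed |

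**Tracing one excluded episode.** Suppose a recorded VT of two minutes at 08:00 receives no shock, and the same patient is shocked for VT/VF at 20:00. The gap is 12 hours.

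- 8.3.3 excludes the 08:00 episode.
- 8.3.2 concerns treatments. It reviews data from defibrillations and other cardiac events, so the episode may be looked at, but no count of unshocked episodes is promised.
- 8.3.5 concerns arrhythmias other than VT/VF.
- 8.3.4 and 8.3.6 capture the episode only if it leads to arrest or death.
- The adjudication described in 8.3.2 and 8.3.3 covers shocked events, terminal recordings and the 8.3.3 episodes. This one is in none of those groups.
- 6.3.1.1 does have the site notified of it.

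The episode is therefore captured but has no assured place in the tables.

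**Tracing one unflagged episode.** Suppose VT of at least 30 seconds is visible on a recording but set off no alarm or detection, with no shock within 24 hours. By 3.3.1.3 it is not a sustained arrhythmia and is not counted. By the text of 8.3.3 it is unshocked VT of sufficient duration and is counted. Both readings have support.

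**Size, under assumed shares only.** Let c be the share of untreated sustained episodes that fall within 24 hours of a shocked event, and m the share that are unflagged, taken as independent. Under the stricter reading, the share lost from the 8.3.3 count is 1 − (1 − m)(1 − c).

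- c = 0, m = 0: loss 0%.
- c = 10%, m = 0: 1 − 1 × 0.9 = 10%.
- c = 30%, m = 10%: 1 − 0.9 × 0.7 = 37%.
- c = 50%, m = 30%: 1 − 0.7 × 0.5 = 65%.

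If the duration wording of 8.3.3 governs instead, m drops out and the loss equals c. Neither c nor m is given in the documents, so these figures show only how the two rules combine.

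**The case against.** The strongest reply is that 8.3.3 is by design the endpoint for events unrelated to a shock. Grouping clustered episodes with an index shock is a recognisable choice, and the surrounding episodes may be reviewed under 8.3.2. The most serious missed episodes can still surface as SCA, as deaths or in terminal ECG review. All of this is fair, and it means that the data are not lost. It does not put the episodes into any promised count, and neither 2.2.1 nor 3.3 mentions the restriction.

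Four stronger readings are tempting, and the documents do not support them.

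- *The plan overstates effectiveness.* A reader might take 250 × 1.5% = 3.75 expected shocked patients from 8.1.1 and reason that one excluded episode turns 4 of 4 into 4 of 5 (80%), and two into 4 of 6 (67%). The protocol defines no such ratio; 8.3.2 evaluates effectiveness descriptively. The 250 refers to the extended-wear group alone and yields patients, not episodes, whereas the registry of up to 1400 also collects defibrillation data.
- *Untreated means failed.* Section 1.4.2 describes the response buttons as a check of consciousness, with a shock only if the patient does not respond. A conscious patient who withholds the shock is the device working as intended.
- *Undetected episodes are clearly excluded.* The detection condition stands in 3.3.1.3, not in 8.3.3. This is a conflict between sections.
- *Episodes shocked before 30 seconds vanish.* They are still counted as treatments, because 3.3.1.4 sets no minimum duration.

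**Conclusion.** The point holds as a mismatch between objective and analysis, together with a conflict of definitions. The 24-hour exclusion is explicit in 8.3.3 and absent from 2.2.1 and 3.3, and no other endpoint undertakes to count what it removes. Whether recorded but unflagged VT/VF counts depends on whether 3.3.1.3 or 8.3.3 is followed.

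The size cannot be derived from the documents. It is zero if no untreated sustained episode falls within 24 hours of a shocked event and none goes unflagged. The endpoint is secondary and descriptive, no hypothesis test depends on it, and the primary endpoint is unaffected. The change is still worth making: these are likely to be small counts, where one reclassified episode can show, and the remedy lets the study deliver its own objective. The conclusion rests on reading the 24-hour rule as written, in both directions, and on taking 8.3.2 to promise review but no tally of unshocked episodes.

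**What to change.** 1. In 8.3.3, count all untreated sustained VT/VF on WCD recordings. Report those within 24 hours of a shocked event on a separate line, with the number of episodes and the number of patients, so that clusters remain visible without dominating the total.
2. Break both lines down by reason for no shock, using the categories 8.3.3 already names: "including response button use, rate threshold settings, or ECG artifact".
3. Align 3.3.1.3 with 8.3.3 by defining sustained VT/VF from adjudicated ECG on the available WCD recordings, whether or not the device alarmed. State that the episodes within 24 hours of a shock, and the unflagged ones, also go to the committee.
4. Do not use treated plus untreated episodes as a pooled effectiveness denominator.

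If the team prefers to keep the exclusion, 2.2.1 and 3.3 should be narrowed to match and the reason given.

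The cost is wording in 3.3.1.3 and 8.3.3, some additional strips to adjudicate, and a possibly higher untreated count. The documents do not say how much unflagged ECG is stored or reviewed, so the definition should be confined to available recordings; it should not imply a search of continuous ECG.
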